### **Time to Return to Normal Health and Activity**

Time to return to normal health and activity will be summarized using descriptive statistics, as well as Kaplan-Meier plots.

Time to return to normal health and activity as defined by a 'Yes' response to the following question on the CARIFS: "Since the last assessment has the patient been able to return to day care/school or resume his or her normal daily activity in the same way as performed prior to developing the flu?" and remaining so for at least 21.5 hours.

Patients who do not return to normal health and activity will be censored at the last observation time point.

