4.1.1 Inclusion Criteria

Patients must meet the following criteria for study entry:

- Written informed consent for study participation obtained from patient's parents or legal guardian
- Age from birth to <1 year at screening
- Parent/guardian willing and able to comply with study requirements, in the investigator's judgment
- Patients with a diagnosis of influenza virus infection confirmed by the presence of **all** of the following:
 - *In the investigator's judgement there is a clinical suspicion of influenza*
 - At least one respiratory symptom (either cough or coryza)
 - Positive prescreening influenza test (RIDT or PCR) performed within *48 hours of screening*

Results from local testing as part of standard of care are acceptable if samples are collected within 48 hours of screening and recorded in the patients' medical records.

- Patients with a negative prescreening COVID-19 test (*RAT or PCR*) *within 48 hours of screening*

Results from local testing as part of standard of care are acceptable if samples are collected within 48 hours of screening and recorded in the patients' medical records.
- The time interval between the onset of symptoms and screening is ≤ 96 hours (the onset of symptoms is defined as the time when body temperature first exceeded 37.5°C if known, or the time when the first symptom was noticed by the parent or caregiver)

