### **Time to Alleviation of Influenza Signs and Symptoms**

Time to alleviation of influenza signs and symptoms (TTAS) in hours, will be summarized using descriptive statistics, as well as Kaplan-Meier plots. It is defined as the length of time taken from the start of treatment to the point at which all of the following criteria are met and remain so for at least 21.5 hours:

- A score of 0 (no problem) or 1 (minor problem) for cough and nasal symptoms (items 14 and 15 of the CARIFS questionnaire, see [Appendix 4](#)).
- A “yes” response to the following question on the CARIFS: “Since the last assessment has the subject been able to return to day care/school, or resume his or her normal daily activity in the same way as performed prior to developing the flu?”
- Return to afebrile state (tympanic temperature  $\leq 37.2^{\circ}\text{C}$ ).

If a score of 4 (“Don’t Know/Not Applicable”) occurs at any assessment during the study for items 14 or 15, the assessment will not be included in the calculation of the alleviation of symptoms because the assessment was unobservable.

Patients with symptom scores  $\leq 1$  for both items 14 and 15, as well as tympanic temperature  $\leq 37.2^{\circ}\text{C}$  and a “yes” response to the question “Since the last assessment has the subject been able to return to day care/school, or resume his or her normal daily activity in the same way as performed prior to developing the flu?” simultaneously at baseline will be excluded from the analysis.

Patients who do not experience alleviation of symptoms prior to completion or withdrawal from study will be censored at the last observation time point.

Baseline is defined as the first CARIFS assessment on Day 1 after the start of treatment. Patients who do not have a CARIFS assessment on Day 1 after the start of treatment will have their baseline CARIFS assessment set to missing.

The number of patients with completed CARIFS as well as the number with missing CARIFS per assessment will be presented for the ITT and ITTi sets. Additionally, the number and percentage of those with “Don’t Know/ Not Applicable” per question per assessment will be presented for the ITT and ITTi sets.

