### **Duration of Fever**

Duration of fever will be summarized using descriptive statistics, as well as Kaplan-Meier plots. It is defined as the time to return to afebrile state (tympanic temperature  $\leq 37.2^{\circ}\text{C}$ ) and remaining so for at least 21.5 hours.

Patients who do not return to afebrile state will be censored at the last observation time point.

Patients who are afebrile at baseline (tympanic temperature  $\leq 37.2^{\circ}\text{C}$ ) or whose body temperature is not collected will be excluded from the analysis.

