### **Duration of Symptoms**

Duration of symptoms will be summarized using descriptive statistics, as well as Kaplan-Meier plots. Duration of symptoms is defined as alleviation of all symptoms as defined by a score of 0 [no problem] or 1 [minor problem] and remaining so for at least 21.5 hours, for all 18 symptoms specified in the CARIFS questionnaire.

If a score of 4 (“Don’t know/Not Applicable”) occurs at any assessment during the study for any item, with the exception of items 10, 11, and 12, the assessment will not be included in the calculation of the duration of symptoms because the assessment was unobservable.

However, if a score of 4 occurs for items 10, 11, or 12, the assessment will be included, with a score of missing for these items.

All patients will be included in the analysis, regardless of their symptoms at baseline.

In addition, duration of individual symptoms will be summarized using descriptive statistics, as supportive analysis, with the exception of items 10, 11, and 12. If a score of 4 (“Don’t know/Not Applicable”) occurs for the individual symptom at any assessment during the study the assessment will not be included in the calculation of the duration of that individual symptom. Patients who have an individual symptom score  $\leq 1$  at baseline will have the duration of that symptom set to missing.

In the main analysis of the duration of symptoms, only complete assessments (i.e., assessments that have responses for all 18 symptoms in the CARIFS questionnaire) that do not contain a score of 4 for any items, with the exception of items 10, 11, and 12, are considered. A sensitivity analysis will be conducted that considers all assessments in the calculation of the duration of symptoms, where a score of 4 does not break the

incidence of alleviation for items other than 10, 11, and 12, and a score of 4 is considered alleviation for items 10, 11, and 12.

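### Time to return to normal activity has no baseline rule and duration of symptoms keeps every infant, so infants already in the end state at the Day 1 assessment shorten both medians

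*SAP*

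**What the plan says.** All references are to SAP 4.3.1 unless stated. Efficacy is analysed in the ITTi set, and time-to-event and duration endpoints are summarised by Kaplan-Meier plots and medians.

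- **Time to return to normal health and activity.** The event is "Time to return to normal health and activity as defined by a 'Yes' response to the following question on the CARIFS", lasting at least 21.5 hours. The only handling rule is "Patients who do not return to normal health and activity will be censored at the last observation time point". Nothing is said about infants at 'Yes' at baseline, so the ITTi default keeps them.
- **Duration of symptoms.** "Duration of symptoms is defined as alleviation of all symptoms as defined by a score of 0 [no problem] or 1 [minor problem", again held for 21.5 hours, for all 18 items. Retention is explicit: "All patients will be included in the analysis, regardless of their symptoms at baseline".
- **TTAS.** Infants who meet every criterion "simultaneously at baseline will be excluded from the analysis".
- **Duration of fever.** "Patients who are afebrile at baseline" are left out.
- **Individual symptoms.** Infants scoring 1 or less "at baseline will have the duration of that symptom set to missing".

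The CARIFS baseline is the first assessment on Day 1 after treatment starts, and it is missing if there is none that day. The schedule of activities places the first CARIFS after dosing.

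Protocol 4.1.1 requires clinical suspicion, a positive influenza test and "At least one respiratory symptom (either cough or coryza". It sets no minimum severity, requires neither fever nor loss of normal activity, and allows up to 96 hours since onset.

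**The concern.** Neither event definition requires a change of state. An infant with a minor cough who feeds and plays normally can enrol, be at 'Yes' (or have all rated items at 0 or 1) at the first entry, and stay there. That infant meets the definition at the first entry, hours after dosing. The 21.5-hour rule screens out only those who worsen within that time.

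A reader will take a time to return as the speed of recovery after baloxavir. Part of the reported median would instead reflect how many infants had nothing left to recover from when first assessed. This single-arm study has no control group to show the difference.

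No planned analysis of these two endpoints isolates the effect. The sensitivity analysis for duration of symptoms deals only with scores of 4, and return to normal activity has none. The CARIFS counts that the SAP specifies cover completed, missing and 'Don't Know/Not Applicable' responses. The share already in the end state is not among them.

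**Working it through.** **Nothing to reproduce.** The documents give no expected median, sample-size calculation or power for these endpoints. The check is a comparison of rules followed by an illustration of size.

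**Rules for infants already in the end state at baseline**

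| Endpoint | Rule |
|---|---|
| TTAS | excluded |
| Duration of fever | excluded |
| Individual symptoms | set to missing |
| Duration of symptoms, all 18 items | kept, stated |
| Return to normal activity | kept, by silence |

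**Inputs for the illustration**

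- r, the share already in the end state at baseline and remaining so: not in the documents. Assumed 5% to 50%.
- M, the median in the remaining infants: assumed 44.6 h, borrowed from a related endpoint in the Japanese pediatric study (Protocol 1.2.4). The percentage changes below do not depend on M.
- Time origin: start of treatment. The SAP states this for TTAS and does not restate it for these two endpoints.

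**Formula.** If the share r has its events before the pooled median t, then t solves (1 − r) × S(t) = 0.5, where S is the survival curve of the remaining infants.

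- Exponential: t = M × [1 + log2(1 − r)]
- Weibull with shape k: t = M × [1 + log2(1 − r)]^(1/k)
- Lognormal with log-SD 0.6: t = M × exp(0.6 × z), where z is the standard normal quantile at 1 − 0.5/(1 − r)

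Example at r = 20%: 1 + log2(0.8) = 0.678. The exponential gives 44.6 × 0.678 = 30.2 h, a fall of 32%. The Weibull with k = 2 gives 44.6 × √0.678 = 36.7 h, a fall of 18%.

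**Pooled median in hours, against 44.6 h in the infants not yet in the end state**

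| r | Exponential | Weibull 1.5 | Weibull 2 | Lognormal | Fall |
|---|---|---|---|---|---|
| 5% | 41.3 | 42.4 | 42.9 | 42.9 | 4–7% |
| 10% | 37.8 | 40.0 | 41.1 | 41.0 | 8–15% |
| 20% | 30.2 | 34.4 | 36.7 | 36.8 | 17–32% |
| 30% | 21.7 | 27.5 | 31.1 | 31.8 | 29–51% |
| 40% | 11.7 | 18.3 | 22.9 | 25.0 | 44–74% |

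At r of 50% or more the median falls among the first entries themselves.

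**Check at the planned size.** 20,000 simulated trials were run with n = 30, Weibull shape 1.5, and event times of infants already in the end state spread evenly over 0.5 to 12 h. Mean sample medians with these infants kept, against excluded, were 40.2 and 45.0 h at r = 10%, 34.6 and 45.1 h at 20%, and 27.8 and 45.0 h at 30%. This agrees with the Weibull 1.5 column.

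**The case against.** **Keeping everyone is a legitimate choice.** For duration of symptoms it is stated outright, beside a different rule for individual symptoms, so the authors evidently meant it. This stands. A reader might infer an oversight there, but the text does not support that. The SAP is silent only for return to normal activity.

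**The infants may have been ill.** A reader might infer that an infant at 'Yes' at the first entry never left normal activity. The documents cannot show this. Every CARIFS entry is post-dose, and enrolment is allowed up to 96 hours after onset. Such an infant may have lost normal activity and regained it before the first entry. What can be said is that no return was observed in either case.

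**Exclusion conditions on a post-treatment value.** Dropping infants by a post-dose answer may remove very early responders and lengthen the median. This also stands, and it is why the all-infant result must remain on view. It does not defeat the restriction, because TTAS already uses the same post-dose CARIFS baseline, and the body temperature baseline in SAP 4.2.1.5 is also post-dose.

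**It would show in the plots.** A block of early events would appear as a step in the Kaplan-Meier curve. The reported median would still include it, and a step does not show how many infants were in the end state at baseline.

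**Little hangs on it.** Both endpoints are secondary and descriptive, in a study of about 30 infants, and the key efficacy endpoint, TTAS, is protected by its own exclusion. This limits the consequence to interpretation.

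**Conclusion.** The point holds. As written, infants in the end state at the Day 1 baseline who stay there for 21.5 hours are counted as recovering within hours, and both medians can only be shortened by this. The direction follows from the definitions, given a clock that starts at treatment.

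The size cannot be fixed from the documents. The falls of 8–15%, 17–32%, 29–51% and 44–74% at r = 10%, 20%, 30% and 40% rest on assumed shares and distributions. The top of each range is the exponential case and should not be read as the estimate. Nor need r be the same for both endpoints: a single 'Yes' is a different condition from all rated items at 0 or 1.

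A reader might also infer that the medians would measure only how mild the enrolled infants were. That goes too far. Below r = 50% the median depends on both mildness and the speed of recovery in the others.

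**What to change.** In SAP 4.3.1:

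1. For both endpoints, report the number and percentage of infants already in the end state at the SAP-defined baseline, the first CARIFS on Day 1 after treatment.
2. For time to return to normal health and activity, apply the same kind of baseline exclusion as for TTAS and fever, here to infants at 'Yes', and show the all-infant Kaplan-Meier result beside it.
3. For duration of symptoms, keep the stated all-patient analysis and add a Kaplan-Meier median restricted to infants with any rated item of 2 or 3 at baseline.
4. Do not exclude an infant with a missing Day 1 CARIFS on the strength of a later first entry, since that infant may have taken a day or more to recover. Keep such infants in the all-infant version and report their number.

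The cost is SAP wording and one further Kaplan-Meier analysis per endpoint, with no new data. The restricted sets will be smaller, drawn from about 30 infants, and may lose some very early responders. The all-infant results keep those visible.

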### **Frequency of Influenza-Related Complications**

The number of influenza-related complications, as well as the number and percentage of patient with these complications, after treatment, will be presented. Influenza-related complications include death, hospitalization, radiologically-confirmed pneumonia, bronchitis, sinusitis, otitis media, encephalitis/encephalopathy, febrile seizures and myositis, as recorded on the AE pages of eCRF.

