ITT	intent-to-treat
ITTi	intent-to-treat influenza-infected
IxRS	interactive voice or web-based response system
LPLV	last patient, last visit
M2	matrix-2
NA	neuraminidase
NCI	National Cancer Institute
NCI CTCAE	National Cancer Institute Common Terminology Criteria for Adverse Events
NONMEM	non-linear mixed-effects model
Own	otherwise healthy
PCR	polymerase chain reaction
PK	pharmacokinetic
PKEP	pharmacokinetic-evaluable patient

Abbreviation	Definition
PRO	patient-reported outcome
QTc	corrected QT interval
RAT	rapid antigen test
RIDT	rapid influenza diagnostic test
RT-PCR	reverse transcription-polymerase chain reaction
TCID ₅₀	50% tissue culture infectious dose
Vc/F	apparent volume of distribution for the central compartment
ULN	upper limit of normal

1. **BACKGROUND**

1.1 **BACKGROUND ON INFLUENZA**

Influenza is an acute respiratory infectious disease caused by a virus of the orthomyxovirus family. Two forms are known to infect humans: influenza A and B. These viruses cause an acute febrile infection of the respiratory tract after an incubation period of 1 to 4 days, characterized by the sudden onset of fever, cough, fatigue, headache, and myalgia. *Some may experience vomiting and diarrhea, although this is more common in children than adults, and others may be infected with influenza and have respiratory symptoms in the absence of fever (CDC 2011).* Annual influenza epidemics are thought to result in between 3 to 5 million cases of severe illness and between 250,000 and 500,000 deaths every year around the world (WHO 2018).

Although the condition is usually self-limiting in healthy adults, it can be associated with substantial morbidity and occasional mortality in children, the elderly, and the immunocompromised (Paules and Subbarao 2017). Children play a central role in the dissemination of influenza in the community by virtue of their relative serosusceptibility and consequently higher illness attack rates. In addition to the acute illness, young children are at particular risk of secondary bacterial infections. Children develop more severe disease compared with adults, with higher hospitalization rates particularly in children aged <5 years (Rotrosen and Neuzil 2017).

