5.2.1 Adverse Events

According to the ICH guideline for Good Clinical Practice, an adverse event is any untoward medical occurrence in a clinical investigation patient administered a pharmaceutical product, regardless of causal attribution. An adverse event can therefore be any of the following:

- Any unfavorable and unintended sign (including an abnormal laboratory finding), symptom, or disease temporally associated with the use of a medicinal product, whether or not considered related to the medicinal product
- Any new disease or exacerbation of an existing disease (a worsening in the character, frequency, or severity of a known condition) (see Section [5.3.5.8](#) and Section [5.3.5.9](#) for more information)
- Recurrence of an intermittent medical condition (e.g., headache) not present at baseline
- Any deterioration in a laboratory value or other clinical test (e.g., ECG, X-ray) that is associated with symptoms or leads to a change in study treatment or concomitant treatment or discontinuation from study drug
- Adverse events that are related to a protocol-mandated intervention, including those that occur prior to assignment of study treatment (e.g., screening invasive procedures such as biopsies)

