5.3.5.9 Lack of Efficacy or Worsening of Influenza

Medical occurrences or symptoms of deterioration that are anticipated as part of influenza, such as fluctuation in symptoms, should only be recorded as an adverse event if judged by the investigator to have unexpectedly worsened in severity or frequency or changed in nature at any time during the study. When recording an unanticipated worsening of influenza on the Adverse Event eCRF, it is important to convey the concept that the condition has changed by including applicable descriptors (e.g., "accelerated worsening of influenza").

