5.3.5.10 Hospitalization or Prolonged Hospitalization

Any adverse event that results in hospitalization (i.e., inpatient admission to a hospital) or prolonged hospitalization should be documented and reported as a serious adverse event (per the definition of serious adverse event in Section 5.2.2), except as outlined below.

An event that leads to hospitalization under the following circumstances should not be reported as an adverse event or a serious adverse event:

- Hospitalization for respite care
- Hospitalization for a preexisting condition, provided that all of the following criteria are met:
 - The hospitalization was planned prior to the study or was scheduled during the study when elective surgery became necessary because of the expected normal progression of the disease
 - The patient has not experienced an adverse event

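### Influenza admissions, and events a site regards as part of influenza, can go unrecorded because the complication endpoint is read only from adverse event pages that depend on investigator judgement

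*SAP*

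**What the plan says.** - **SAP 4.3.1, Frequency of Influenza-Related Complications.** The definition begins "Influenza-related complications include death, hospitalization, radiologically-confirmed pneumonia, bronchitis, sinusitis, otitis media", goes on to encephalitis or encephalopathy, and ends "febrile seizures and myositis, as recorded on the AE pages of eCRF". Events after treatment are counted. No complications form, admission record or adjudication is named as a further source.
- **Protocol 5.3.5.9.** The rule concerns "Medical occurrences or symptoms of deterioration that are anticipated as part of influenza, such as fluctuation in symptoms". These "should only be recorded as an adverse event if judged by the investigator to have unexpectedly worsened in severity or frequency or changed in nature". Fluctuating symptoms are the only example given, and the term is not defined further.
- **Protocol 5.3.5.10.** The rule begins "Any adverse event that results in hospitalization (i.e., inpatient admission to a hospital) or prolonged hospitalization should be documented and reported as a serious adverse" (that is, as an SAE). The exceptions are respite care, and planned or elective admission for a pre-existing condition when no adverse event has occurred. Protocol 5.2.2 is built the same way: needing or lengthening an inpatient stay makes an adverse event serious.
- **Protocol 5.3.5.7.** Every death in the reporting period goes on the Adverse Event eCRF, and deaths from influenza progression are expressly included.
- **Protocol 4.1.2.** Infants already in hospital for observation, monitoring or precautionary care may be enrolled.

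**The concern.** The endpoint depends entirely on a set of pages whose content another rule restricts. If an investigator regards an event as part of the expected course of influenza, 5.3.5.9 allows it to stay off the page. An admission then has nothing to attach to, because 5.3.5.10 and 5.2.2 start from an adverse event, and a hospital stay is not itself a disease. Protocol 1.1 gives a site some reason to see complications as unsurprising: it says that "young children are at particular risk of secondary bacterial infections" and notes higher hospitalization rates in children under 5 years.

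Two outputs are exposed: the secondary complication endpoint, and the adverse event and serious adverse event tables that carry the primary safety objective. The SAP also limits the antibiotics endpoint to use for influenza-related complications, so that endpoint may inherit the gap. The study has a single arm, so no comparator shares any under-recording. About 25 sites (Protocol 9.4) would each be deciding what counts as expected.

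**Working it through.** **Step 1: trace each listed complication to the page.**

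| Event | What brings it onto the adverse event page | Can 5.3.5.9 keep it off? |
|---|---|---|
| Death | 5.3.5.7, explicit; SAP 4.1 also takes deaths from all sources in safety analyses | No |
| Otitis media, radiologically confirmed pneumonia, sinusitis, encephalitis or encephalopathy, myositis | New disease (5.2.1); record the diagnosis (5.3.5.1); new examination abnormality (4.5.3); change in nature (5.3.5.9 itself) | Unlikely |
| Bronchitis, febrile seizure | The same rules, but a site may see either as part of a febrile respiratory illness | Possible |
| New admission for influenza judged to be on its expected course | 5.3.5.10 and 5.2.2, only if an adverse event led to it | Possible |
| Lengthened stay in an infant already in hospital at dosing | As above; neither document says how a stay under way at dosing is counted | Possible |

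The gap is therefore confined to the last three rows. Only death has a rule that expressly overrides the view that the event was to be expected.

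**Step 2: size per infant.** The plan states no complication rate, so there is no figure of its own to reproduce. Protocol 6.2 gives about 30 infants. One infant whose only complication goes unrecorded moves the proportion by 1/30 = 3.3 percentage points. The influenza-infected analysis set may be smaller than 30, which would make the step larger.

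**Step 3: illustration under assumptions.** Let p be the true proportion of infants with a complication, and u the share of those infants for whom nothing is recorded. Neither comes from the documents.

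- Expected number counted = 30 × p × (1 − u)
- Chance of counting at least one = 1 − (1 − p(1 − u))^30

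| Assumed p | u = 0 | u = 25% | u = 50% |
|---|---|---|---|
| 5% | 1.5 infants; 78.5% | 1.13; 68.2% | 0.75; 53.2% |
| 10% | 3.0; 95.8% | 2.25; 90.4% | 1.5; 78.5% |
| 20% | 6.0; 99.9% | 4.5; 99.2% | 3.0; 95.8% |

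For example, with p = 5% and u = 50%, 1 − 0.975^30 = 53.2%. Since Step 1 keeps most new diagnoses on the page, u depends on how many infants have only events from the last three rows.

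**Step 4: set against sampling error.** Clopper-Pearson 95% intervals at n = 30 are 0 to 11.6% for 0/30, 0.1 to 17.2% for 1/30, and 2.1 to 26.5% for 3/30. A loss of one or two infants lies within that imprecision, but it acts in one direction only and the interval does not reflect it.

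**The case against.** A reader might infer that the protocol instructs sites to leave complications and influenza admissions off the adverse event pages, that they are lost as a class, and that nothing else would bring them into the data. The documents do not support this:

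- 5.3.5.9 mentions neither complications nor admissions, and it still requires recording when an event is unexpectedly worse or changed in nature.
- 5.2.1 makes any new disease an adverse event, and 5.3.5.1 asks for the diagnosis.
- 4.5.3 sends new or worsened clinically significant examination findings to the Adverse Event eCRF with no exemption for expected events. Examinations are scheduled on Days 2, 4, 6, 10 and 29, and 4.5.2 asks for an interval history at each follow-up examination.
- 5.3.5.5 requires an abnormal vital sign to be reported if it leads to intervention or a change in concomitant therapy. Antibiotics would appear on the Concomitant Medications eCRF.
- Protocol 1.1 describes risk in young children; it does not classify complications as expected in the sense of 5.3.5.9. Protocol 5.1 says eligibility was designed to exclude infants at higher risk of serious influenza.
- In the earlier Phase III study of patients aged 12 to 64 (Protocol 1.2.3), bronchitis and sinusitis were reported as adverse events, although the documents do not say what recording rule applied there.
- An unplanned influenza admission falls under neither exception in 5.3.5.10, and many investigators would call an illness that comes to need admission unexpectedly worse.

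Most of this stands and narrows the point. It does not close it. The new-disease bullet in 5.2.1 itself refers the reader to 5.3.5.9. The exceptions in 5.3.5.10 matter only once an adverse event exists. Medication records are not a source for the endpoint. No sentence settles the case of an expected-course admission, a prolonged stay, or a febrile seizure or bronchitis seen as part of influenza. Nor can one say that the Internal Monitoring Committee would be blind to such events, because its charter is not among the documents; the eCRF completion manual is also unseen and may contain further instructions.

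**Conclusion.** The point holds in a limited form. Capture of influenza admissions, prolonged stays, febrile seizure and bronchitis rests on each investigator's view of what is to be expected, and a site can follow the written rules and record none of them. Where that happens, the complication proportion and the adverse event and serious adverse event counts are too low, never too high, and sites may differ. Deaths are safe, and new diagnoses such as otitis media, pneumonia, sinusitis, encephalitis and myositis should be recorded.

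The only size that can be stated is 3.3 percentage points per infant at n = 30. The total loss may be nil; the table in the working shows what assumed rates would imply and is not an estimate. The analyses are descriptive and no hypothesis test is affected. The change is still worth making, because a stated recording rule works against a stated endpoint in one direction and the remedy is cheap.

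**What to change.** **Protocol 5.3.5.9.** Add that the influenza-related complications listed in Section 2, and any unplanned admission or prolongation of a stay after dosing for influenza or its complications, are always recorded on the Adverse Event eCRF, whether or not they were to be expected. Leave the respite-care and planned or elective exceptions in 5.3.5.10 as they are.

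**SAP 4.3.1.** Define hospitalization as a new admission, or a prolongation of a stay, after dosing that is due to influenza or a listed complication. State that a stay already under way at dosing is not counted unless it is prolonged. The seriousness criterion alone would not do as the definition, because it would also count admissions unrelated to influenza.

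**Cost.** One sentence in a protocol amendment and a short addition to the SAP; a few more adverse event pages; and possibly a somewhat higher reported rate of adverse events, serious adverse events and complications. The change concerns what is recorded and counted, not how infants are treated. The recording rule acts only from the date it takes effect.
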